6.3. Study Population

6.3.1. Subject Disposition

Subject disposition will be presented by treatment group and overall, including the number screened, the number of screen failures, the number randomized and the number who received study vaccine administration. The study disposition will also be presented along with the reasons for early study withdrawal.

The number of subjects in each analysis set will be presented on the Randomized Population by treatment group and overall.

The following by-subject listings will be presented.

- Study completion information, including the reason for premature study withdrawal
- Visit dates
- Inclusion in study Analysis Sets and reason for exclusion from the IEP
- Protocol deviations

6.3.2. Demographic Characteristics

Demographic characteristics at enrollment (i.e., at the time of informed consent) will be presented. Summary will include the following: age, sex, ethnicity, race, height, weight, body mass index.

Medical history will be coded using Medical Dictionary for Regulatory Activities (MedDRA) and summarized alphabetically by System Organ Class (SOC) and Preferred Term (PT).

Childbearing potential and method of contraception will be presented in Listings only.

Table summaries to be produced by treatment group and overall and repeated for the following:

Populations: RND, SAF, IEP

Subgroups: 18-64, 18-49, 50-64

Demographic characteristics and medical history data will also be provided in data listings on the Randomized Population.

6.3.3. Prior and Concomitant Medication

Prior and concomitant medications will be coded using the WHO Drug dictionary.

Prior medications will be defined as any medications with a start date before the date of study vaccine administration.

Concomitant medications will be defined as any medications with a start date on or after the date of study vaccine administration, as well as medications taken prior to the study vaccine administration and continuing after.

If a medication date or time is missing, or partially missing, and it cannot be determined whether it was taken on or after start of treatment, it will be considered a concomitant medication.

Results will be tabulated by Anatomic Therapeutic Class level 2 and preferred term.

Table summaries to be produced by treatment group and overall and repeated for the following:

Population: SAF

Subgroups: 18-64, 18-49, 50-64

Prior and concomitant medications will be included in a by-subject data listings.

6.3.4. Exposure and Compliance

Frequency and percentage of subjects with vaccinations will be summarized. For subjects who received a vaccine, the administered vaccine will be summarized.

Table summary to be produced by treatment group and repeated for the following:

Population: RND

Subgroups: 18-64, 18-49, 50-64

6.4. Efficacy Evaluation

Not Applicable.

6.5. Safety Evaluations

All Safety summaries to be produced by treatment group, for the following:

Population: SAF

Subgroups: 18-64, 18-49, 50-64

Summaries including primary endpoints (noted as [P]), secondary endpoints (noted as [S]) or exploratory endpoints (noted as [E]), will also be repeated for the following:

Population: SAF

Subgroups: 50-59, 60-64

6.5.1. Adverse Events

6.5.1.1. Solicited Adverse Events

Solicited AEs are protocol-specified local and systemic symptoms/events that are proactively collected from the subject and evaluated by the Investigator or designee. Solicited AEs are collected for 7 days after each injection, starting on Day 1, within an electronic diary. All solicited AEs will be considered “Probably related” to study vaccine.

Solicited AEs for this study are:

- Local events: Pain, Erythema (redness) at the injection site, Edema (swelling) at the injection site
- Systemic events: Fever (oral temperature $\geq 100.4^{\circ}\text{F}$), Fatigue, Headache, Muscle pain, Joint pain

The Subject and the Investigator will grade all AEs for severity from “mild” (grade 1) to “potentially life-threatening” (grade 4), except for severity of redness and swelling recorded as diameters (cm) and graded accordingly (see Guidance for Industry Toxicity Grading Scale for Healthy Adult and Adolescent Volunteers Enrolled in Preventive Vaccine Clinical Trials, September 2007 for details on grading scale).

Only Solicited AEs collected in the eDiary CRF, within 7 days after vaccine administration (i.e. from Day 1 to Day 7) will be analyzed in this Section. Occurrence of a solicited AE on a specific Day will be identified by a Grade ≥ 1 for that AE on that day.

Solicited AEs continuing beyond 7 days after injection will be combined with unsolicited AEs and described separately as specified in Section 6.5.1.3.

The following characteristics will be calculated:

- Maximum severity (Investigator):

For each solicited AE collected for a subject, the maximum severity will be the highest grade recorded, as per Investigator, for all occurrences of this AE within 7 days of vaccine administration (i.e., from Day 1 post-administration to Day 7) for the overall summary, or within a single day for the summary by day. There will be no replacement in case of missing Grade.

- Maximum relationship (Investigator):

For each unsolicited AE collected for a subject, the maximum relationship will be the strongest relationship, as per Investigator, for all occurrences of this AE. There will be no replacement in case of missing relationship.

- Time of first onset of first event (days):

Day of onset of the first solicited AE, as per the nominal visit where the first solicited AE was first reported. This will range from 1 (Day 1 = Day of study vaccine administration) to 7 (Day 7).

- Duration of solicited AEs (days):

Number of days between the onset of the solicited AE (i.e. nominal visit of first occurrence of Grade \geq 1) and the end of the solicited AE (i.e. nominal visit when Grade is back to 0).

If there are different occurrences of a same solicited AE within 7 days, the durations will be added up.

For solicited AEs continuing beyond 7 days, the end day of the continuing event will be used as end day for the calculation.

Example: If a subject has a Fatigue starting on Day 2 and finishing on Day 3. And a new Fatigue starting on Day 7 and ending on Day 9. The Duration will be 1+2=3.

If the solicited AE is ongoing (i.e. stop date is missing), then duration will be the Number of days between the onset of the solicited AE and the study discontinuation date.

Frequencies and percentages of subjects experiencing each solicited AE will be presented overall and by maximum severity. Summary tables showing the occurrence of any local or systemic solicited AE overall and at each time point will also be presented. For each of the time points or time intervals presented in the summaries, only subjects with at least one observation (ie, any non-missing values but excluding “Not done/unknown”) for the solicited AEs will be summarized.

The following summaries of subjects will be performed:

- [P] Solicited AEs within 7 days post-injection, for each event and for any event, overall and by maximum severity. Details by category (local, systemic) will also be presented. (Severity as per Investigator)
- Solicited AEs by day post-injection, for each event and for any event, overall and by maximum severity on that day. (Severity as per Investigator)
- Solicited AEs by day post-injection, for each event and for any event, overall and by maximum severity on that day. (Severity as per Subject)

- Time of first onset of solicited AEs within 7 days post-injection for each event and any event. Duration of solicited AEs, after injection, for each event. Maximum duration of any event. (Severity as per Investigator)

Listings of all solicited AEs will be provided by subject.

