## 5.11 Solicited Adverse Events

Solicited AEs will be collected for 7 days after vaccine administration, starting on Day 1. Solicited AEs for this study are local events of pain, erythema (redness) and edema (swelling) at the injection site, and systemic events of oral temperature  $\geq 100.4^{\circ}\text{F}$ , fatigue, headache, muscle pain, and joint pain.

Subjects will be trained to complete a diary via IBM's ePRO system. This system is accessed via a secure URL and will be used to observe, measure, and record these solicited AEs. A digital thermometer will be provided to the subject to measure oral temperature each day, and it is to be recorded daily in the diary. To record injection site local reaction, a ruler will be provided to the subject to measure the diameter of redness and swelling at the largest point of the reaction each day; it is to be recorded daily in the diary.

Study staff will be provided with a Reference Guide for instructing subjects on accessing the IBM ePRO system. Each user will be provided with login credentials and a temporary password. The IBM ePRO system is web-based and accessed via a secure URL.

Study staff will review the signs and symptoms recorded in the diary and the action taken for the event during the subject's clinic visit. The electronic diary will serve as the primary source document and data will be automatically integrated into the subject visit Solicited AE form in the EDC platform for site staff view-only access. The Investigator will then assess all recorded solicited events for severity and relatedness. Severity will be graded according to the FDA Toxicity Grading Scale ([FDA 2007](#)). The results of the Investigator's assessment, if different from the subject's entry, will be recorded in a separate field specified for Investigators within the EDC platform. For solicited injection site reactions, the relationship to study vaccine will be automatically recorded to be probably related, however, the Investigator will determine the relationship for each systemic solicited reaction.

Symptoms continuing beyond the solicited AE collection period (7 days following each injection) will be collected and recorded as an unsolicited AE in the electronic source document (eSD).

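### SAP 6.5.1.1 classes every solicited AE as 'Probably related', against protocol 5.11 and SAP 6.2.6; a smaller point is that protocol 9.6.2's size bands give 2.5 and 5.1 cm no grade

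*SAP*

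**What the plan says.** **Relationship.** SAP 6.5.1.1 assigns 'Probably related' to all solicited AEs. Protocol 5.11 records that category automatically for injection-site reactions only; for each systemic reaction the Investigator decides. Protocol 7.3 has the Investigator assess causality for all AEs, solicited ones included, and protocol 7.6 requires a causality assessment on the SAE Form. SAP 6.2.6 sets a missing relationship for a systemic solicited AE to 'Possibly related'. The maximum-relationship derivation in SAP 6.5.1.1 is written for unsolicited AEs, as per Investigator, with no replacement of a missing value. SAP 6.5.1.2 then lists a primary SAE table by maximum relationship and says that it includes serious solicited AEs. SAP 7 reports no change from the protocol's analyses.

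**Size bands.** Protocol 9.6.2 grades redness and swelling as 0 to 2.4 cm (Grade 0), above 2.5 to 5.0 cm (Grade 1), above 5.1 to 10.0 cm (Grade 2) and above 10.0 cm (Grade 3). Protocol 5.11 says: "Severity will be graded according to the FDA Toxicity Grading Scale". SAP 6.5.1.1 sets these two reactions apart ("except for severity of redness and swelling recorded as diameters (cm) and graded accordingly") and refers to the same 2007 scale without printing cut-offs.

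**Severity grade.** On maximum severity, SAP 6.5.1.1 says: "There will be no replacement in case of missing Grade". The primary solicited table is labelled "Severity as per Investigator". Protocol 5.11 says of the diary: "The electronic diary will serve as the primary source document". It also says: "The results of the Investigator's assessment, if different from the subject's entry, will be recorded in a separate field specified for Investigators".

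**The concern.** The blanket relationship rule replaces an assessment that the protocol gives to the Investigator. If it is programmed as written, a serious fever or headache that the Investigator judged 'Not Related' would appear in a primary safety table as 'Probably related'. It also gives a missing systemic relationship two different values within one SAP, and SAP 7 does not declare the departure.

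The size bands matter because one uncovered value lies on the border between Grade 0 and Grade 1, and that border decides whether an event counts: "Occurrence of a solicited AE on a specific Day will be identified by a Grade" of at least 1. Redness and swelling are part of the first primary endpoint.

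**Working it through.** **Step 1. Set the relationship rules side by side.**

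| Source | Local reaction | Systemic, relationship recorded | Systemic, relationship missing |
|---|---|---|---|
| Protocol 5.11 | Probably (automatic) | Investigator's decision | not addressed |
| Protocol 7.3 | Investigator assesses | Investigator assesses | not addressed |
| SAP 6.5.1.1 | Probably | Probably | Probably |
| SAP 6.2.6 | no rule | no rule | Possibly |

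The last two columns hold the conflict. Where the Investigator recorded 'Not Related' or 'Possibly Related', SAP 6.5.1.1 overrides it. Where nothing was recorded, the SAP gives both 'Probably' and 'Possibly'.

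**Step 2. Find where relationship enters an output.**

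- SAP 6.5.1.1 lists four solicited-AE summaries (within 7 days; by day per Investigator; by day per Subject; onset and duration). None is split by relationship, so no solicited-AE percentage depends on the rule.
- The table of related TEAEs in SAP 6.5.1.2 covers unsolicited events. Solicited events lasting beyond 7 days go to separate summaries in SAP 6.5.1.3, which are not split by relationship.
- The primary SAE table is split by maximum relationship and is the only such table that the SAP says includes solicited AEs. Local reactions are 'Probably related' under both protocol 5.11 and SAP 6.5.1.1, so only serious solicited systemic AEs are exposed.
- For those events the maximum-relationship derivation does not apply as written, because it covers unsolicited AEs. That leaves the blanket rule as the only explicit instruction when a relationship has been recorded.

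The documents give no expected number of serious solicited AEs, so the effect cannot be sized further.

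**Step 3. Check the size bands.** The bands of protocol 9.6.2, coded as printed, are [0, 2.4], (2.5, 5.0], (5.1, 10.0] and above 10.0, enumerated from 0 to 15 cm. Recording precision is not stated, so a range is shown:

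| Recording step (assumed) | Values with no grade |
|---|---|
| 1 cm | none |
| 0.5 cm | 2.5 |
| 0.1 cm | 2.5 and 5.1 |
| 0.01 cm | 2.41 to 2.50 and 5.01 to 5.10 (10 + 10 = 20 values) |

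No value at 0.1 cm falls in two grades. The 2.5 cm gap bears on occurrence. The 5.1 cm gap lies between Grades 1 and 2, so it bears on severity unless it is the subject's only reading.

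For scale only: suppose one subject's deciding reading were exactly 2.5 cm, no other day had a graded reading, and these bands were the ones programmed. That arm's percentage for the reaction would move by 1/16 = 6.25 points in the 18 to 49 cohort or 1/200 = 0.5 points in the 50 to 64 cohort. This is the weight of any one subject, not an estimate of an effect.

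**Step 4. Check the missing-grade rule.** SAP 6.5.1.1 states what happens to a missing grade, and SAP 6.2.6 agrees (no imputation, non-missing denominators). The only thing left unsaid is that a blank Investigator field under protocol 5.11 means agreement with the diary.

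**The case against.** **On relationship.** The override may never happen. The maximum-relationship derivation is labelled as per Investigator, and every SAE Form must carry a causality assessment, so a programmer could simply use that value. This lowers the likelihood but does not remove the contradiction: the derivation is limited to unsolicited AEs, and the sentence covering solicited AEs says the opposite. The objection that almost nothing in the outputs depends on relationship stands in full, and it is why the point is minor. A reader might infer that the blanket rule distorts the primary solicited-AE percentages; Step 2 shows that it does not touch them.

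**On the bands.** The 'greater than' signs may be a slip for 'greater than or equal to'. The bands would then be contiguous at 0.1 cm, though at 0.01 cm the values 2.41 to 2.49 and 5.01 to 5.09 (9 + 9 = 18) would still be uncovered. The SAP also relies on the 2007 scale rather than on protocol 9.6.2. Both arguments stand. A reader might infer that readings will go ungraded in the analysis, or that the SAP changed the size scale without saying so. Neither can be shown, because the cut-offs of the 2007 scale are not in the documents and protocol 5.11 cites that scale too. What remains is a conflict of sources, first of all within the protocol.

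**On blank grades.** A reader might infer that the SAP has no rule for a blank Investigator grade, and that subjects with whom the Investigator fully agreed would drop out of the primary table. The documents do not support this. The SAP has a missing-grade rule and presumes that both Subject and Investigator grade every AE. The denominator sentence keeps "only subjects with at least one observation (ie, any non-missing values", names no rater, and belongs to an analysis of events collected in the eDiary. A blank most naturally means agreement, which has no effect, and how the field is filled depends on completion guidelines that are not among these documents.

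**Conclusion.** The relationship rule in SAP 6.5.1.1 is wrong as written. It contradicts protocol 5.11, protocol 7.3 and SAP 6.2.6, and SAP 7 does not declare it. Its reach is the relationship column for serious solicited systemic AEs in the primary SAE table; the number of such events is unknown and no primary solicited-AE percentage changes.

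The size-band conflict is real but smaller. As printed, protocol 9.6.2 gives no grade to 2.5 or 5.1 cm, assuming recording to 0.1 cm. Neither a frequency nor an effect on a primary percentage can be derived from the documents.

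The meaning of a blank Investigator grade is a matter for optional clarification, not a defect. Confidence is high on the wording conflicts and does not extend to any size of effect. Overall severity: minor.

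**What to change.** 1. **SAP 6.5.1.1, relationship.** Limit the automatic 'Probably related' to solicited local reactions. For systemic solicited AEs use the Investigator's recorded relationship, and apply SAP 6.2.6 only when it is missing. Extend the maximum-relationship derivation to serious solicited AEs on the same basis, keeping 'no replacement' for unsolicited AEs so that the two rules do not collide. If the blanket rule is kept, declare the departure from protocol 5.11 in SAP 7 and remove the unused line from SAP 6.2.6.
2. **Size bands.** Reconcile protocol 9.6.2 with protocol 5.11 and SAP 6.5.1.1. State in both documents one contiguous set of bands for the analysis, with each boundary value in exactly one grade.
3. **Optional line in SAP 6.5.1.1.** State that where the Investigator field is blank, the diary grade stands (for redness and swelling, the grade from the diary diameter).

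The cost is a few SAP sentences, one derivation line and a protocol clarification, with no new data. This is best settled before the interim database lock. The documents do not say whether that lock has passed; if it has, the rules should be recorded before the final lock.

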6.2.6. Missing, Unused, and Spurious Data

Binary endpoints / Continuous data:

Missing data are assumed to be missing at random and ignorable. Missing data will not be estimated or imputed. Denominators for percentages will be based only on the number of subjects with non-missing values. The only exception is:

- Systemic Solicited AEs with missing “Relationship to study vaccine” will be analyzed as “Possibly related”.

Dates:

For partial or missing AE start dates the following imputation rules will be applied:

1. If year is not missing and is after the year of first dose:
 - a. If month is missing, then month will be imputed as January.
 - b. If day is missing, then day will be imputed as the first of the month.

2. If year is not missing and is the same as the year of the first dose:
 - a. If month is missing, then impute the month as the month of the first dose date.
 - b. If day is missing, and the month is the same as the month of the first dose date, then impute day as the day of the first dose date.
 - c. If day is missing but month is after the month of first dose date, then impute day as the first day of the month.
3. If year is missing, then impute the year as the year of the first dose date:
 - a. If month is missing, then impute the month as the month of the first dose date.
 - b. If day is missing, then impute the day as the day of the first dose date.
4. If the start date is completely missing, but the AE is either ongoing (i.e. AE stop date is missing) or the stop date is after the first dose date then impute the start date as the first dose date.
5. For any cases involving the rules above, if the AE end date is before the AE start date, then do not impute the AE start date and assume that the AE is treatment emergent/concomitant for the purpose of the analysis. Further, if the AE stop date occurs prior to the first dose date, do not impute the AE start date, and assume that the AE is not treatment emergent.

No imputations will be applied to AE stop dates or other dates. As indicated above, AEs with missing stop date are considered ongoing.

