6.5.1.2. Unsolicited Adverse Events

An unsolicited AE is an AE that is spontaneously reported by the subject or discovered by the Investigator. New onset of chronic illness(s) would be recorded as part of the collection of unsolicited AEs as specified in the visit procedures. Unsolicited AEs are collected separately from solicited AEs.

Solicited AEs continuing beyond 7 days will be flagged using rules given in Section 5.2 and described in separate summaries as explained in Section 6.5.1.3.

The definition of a treatment emergent AE (TEAE) is an event that occurs after vaccination and within the 28 days after vaccination (i.e., excluding those after a subject has given informed consent, but before vaccination):

- Onset (days) = Start date of AE – Date of Study Vaccine Administration + 1
- An AE is a TEAE if:
 - Onset \geq 1 and Onset \leq 28
 - For AEs with Onset=1 the time of onset of AE must be greater or equal to the time of vaccination to be considered a TEAE

Adverse events are summarized by subject, therefore, in any tabulation, a subject contributes only once to the count for a given adverse event (SOC or preferred term).

Unsolicited AEs will be coded using the Medical Dictionary for Regulatory Activities (MedDRA) and will be summarized by decreasing frequency of SOC and preferred term within SOC in the control group, as follows:

- [P] Any unsolicited TEAEs
- Possibly or probably related unsolicited TEAEs
- Unsolicited TEAEs leading to study withdrawal
- Any AE leading to death
- [P] Any SAE within 6 months after the vaccination by maximum relationship to study treatment. This summary will include serious solicited AEs.
- [P] Any NOCI within 6 months after the vaccination by maximum relationship to study treatment.
- [P] Any MAAEs within 6 months after the vaccination by maximum relationship to study treatment.

Following by-subject Listings will be provided:

- Pre-vaccination AEs (non-emergent)

- All unsolicited TEAEs
- All Serious post-vaccination AEs, NOCIs and MAAEs

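### Unsolicited AEs with no causality rating are never counted as related, while unrated systemic solicited AEs are; the SAE table applies both rules

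*SAP*

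**What the plan says.** SAP 6.5.1.1 is the solicited-AE section, but its definition of maximum relationship is written for unsolicited events: "For each unsolicited AE collected for a subject, the maximum relationship will be the strongest relationship, as per Investigator, for all occurrences of this AE". The next sentence is "There will be no replacement in case of missing relationship".

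SAP 6.2.6 sets the general rule for binary and continuous data, "Missing data will not be estimated or imputed", and allows one exception: "Systemic Solicited AEs with missing “Relationship to study vaccine” will be analyzed as “Possibly related". It has no matching exception for unsolicited AEs, SAEs, NOCIs or MAAEs.

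SAP 6.5.1.2 uses the relationship variable in two ways:
- One table is restricted to related events: "Possibly or probably related unsolicited TEAEs". It is not flagged as a primary-endpoint summary.
- Three summaries that are flagged as primary are broken down by relationship: "Any SAE within 6 months after the vaccination by maximum relationship to study treatment", and the equivalents for NOCIs and MAAEs. The SAE summary also takes in serious solicited AEs.

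On solicited events SAP 6.5.1.1 also says "All solicited AEs will be considered “Probably related” to study vaccine". Protocol 5.11 fixes the relationship in advance only for injection-site reactions and leaves each systemic reaction to the Investigator.

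**The concern.** The protective handling of a missing rating is given to the expected diary symptoms. The events for which a causality signal matters most in a first-in-human study, the unexpected ones, get none. The SAP leans the cautious way elsewhere. In 6.2.6, an AE with no start date that is ongoing or ends after dosing is placed on the dosing date. In 6.3.3, a medication whose timing cannot be determined is treated as concomitant. No reason is given for departing from that pattern here.

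At stake is the count of related unsolicited events by arm, and a consistent meaning for the relationship rows of the SAE table.

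**Working it through.** The plan gives no figure for missing causality, so none can be reproduced. The check sets the rules side by side and then bounds the effect.

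**1. Where an unrated event goes**

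| Event with missing relationship | Rule | Result |
|---|---|---|
| Unsolicited TEAE, every occurrence unrated | SAP 6.5.1.1, no replacement | Absent from the related-TEAE table; still in the all-TEAE table and listing |
| Unsolicited AE, one occurrence not related, another unrated | Strongest available rating | Classed as not related; no missing value shows |
| Unsolicited SAE, NOCI or MAAE, every occurrence unrated | SAP 6.5.1.1 | In the overall count and listing; in no related category |
| Serious systemic solicited AE | SAP 6.2.6 (possibly) or 6.5.1.1 (probably) | Counted as related under either rule |

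The third and fourth rows can both occur in the SAE summary, with opposite results.

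**2. Largest effect per affected subject**

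Inputs: arm sizes of 16 and 200 (Protocol 9.3, Table 4). Suppose a subject's only related event in a row is unrated.
- With the full arm as denominator, the percentage falls by 1/n: 1/16 = 6.3 points, 1/200 = 0.5 points.
- SAP 6.2.6 bases denominators on non-missing values. Read literally, k/n becomes (k − 1)/(n − 1), a fall of (n − k)/[n(n − 1)]. This equals 1/n when k = 1 and is smaller when k > 1.

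So 1/n is a maximum on either reading.

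**3. Direction**

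The related count can only fall. The percentage need not. If the unrated event is truly unrelated and the subject leaves the denominator, 2/16 = 12.5% becomes 2/15 = 13.3%.

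**4. Expected size, under assumptions**

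The documents give neither the true related rate r nor the share m of ratings that are missing. A plausible m after data cleaning is assumed to be 0–1%; 5% and 10% are stress values. Missingness is taken as independent of true relatedness, with one such event per subject. Expected related subjects in an arm of 200 = 200 × r × (1 − m):

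| r | None missing | m = 1% | m = 5% | m = 10% |
|---|---|---|---|---|
| 2% | 4 | 3.96 | 3.8 | 3.6 |
| 5% | 10 | 9.9 | 9.5 | 9 |
| 10% | 20 | 19.8 | 19 | 18 |

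In an arm of 16 with r = 10%, the chance of at least one related event is 1 − 0.9^16 = 81.5%, which agrees with the 81% in SAP 2.2 for a 10% event. Replacing 0.10 by 0.10 × (1 − m) gives 81.1%, 79.8% and 77.9% for m = 1%, 5% and 10%.

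**The case against.** The best defence is that the gap is closed upstream. Protocol 7.3 has the Investigator rate every AE in one of three categories, 7.5.2 lists relationship among the items to record, and 7.6 makes causality mandatory on the SAE form. Data are cleaned before each lock. SAP 6.2.1 says categorical tables show the number of subjects with missing data, which is transparent and the same in every arm. The solicited-AE summaries in 6.5.1.1 are not broken down by relationship, so the 6.2.6 exception has little visible effect outside the SAE table.

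Most of this stands, and it is why the point is minor. It does not remove it. The SAP plans for a missing relationship and resolves it in opposite ways. A missing count does not reveal an unrated occurrence masked by one rated not related, and a table limited to related events has no natural place for an unrated one.

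It might also be said that the no-replacement sentence is misplaced. It is, but the general rule in 6.2.6 gives the same result for unsolicited AEs.

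Three stronger readings are tempting, and the documents do not support them:
- **Unrated SAEs, NOCIs or MAAEs drop out of their tables, or bias the primary endpoint.** The endpoint is the percentage reporting any such event, and they remain in it.
- **Related percentages can only fall.** Step 3 of the working shows that this holds for counts only.
- **The stopping rules are weakened.** Protocol 7.10 does not refer to this tabulation rule, and the Phase 1 SAE criterion applies regardless of relationship.

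**Conclusion.** The point holds as a minor inconsistency. An unsolicited TEAE unrated on every occurrence is excluded from the related-TEAE table. An unrated unsolicited SAE, NOCI or MAAE is counted but never as related. The SAE table mixes this with the opposite rule for serious systemic solicited events. Only the related count is biased in a known direction, downwards, by at most one subject per affected subject with no other related event in that row. At an assumed 0–1% of missing ratings, the expected loss in an arm of 200 is at most 0.2 of a subject, even at a 10% related rate (20 − 19.8). Primary-endpoint percentages are unaffected.

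A linked defect should be settled at the same time. The SAP calls all solicited AEs probably related in 6.5.1.1 and treats unrated systemic ones as possibly related in 6.2.6, while Protocol 5.11 leaves systemic causality to the Investigator. These statements do not agree.

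**What to change.** - In SAP 6.2.6 and 6.5.1.2, state that any AE occurrence, solicited or unsolicited and including SAEs, NOCIs and MAAEs, with a missing relationship is analysed as possibly related. Applying this per occurrence, before the maximum is taken, also removes the masking.
- Footnote each relationship table with the number of ratings imputed.
- Delete the no-replacement sentence for relationship from 6.5.1.1 and move the definition of maximum relationship to 6.5.1.2.
- Reconcile the statement in 6.5.1.1 on the causality of all solicited AEs with SAP 6.2.6 and Protocol 5.11.
- Protocol 9.6.3 counts the strongest reported relationship, so record the imputation in SAP Section 7, which at present declares no changes.

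This costs a few sentences and one footnote and needs no new data. It should be settled before the interim lock for the Day 29 Analysis. The downside is a slightly higher related-AE count, made visible by the footnote.
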